### 6.7.2 Normal tissue constraints for ultrahypofractionated prostate radiotherapy:

The irradiation regimen used in this study is derived from the PACE-B trial, which involved fractionation of 5 x 7.25 Gy up to a total dose of 36.25 Gy (however, with a boost to the prostate (=CTV) of 5 x 8.0 Gy up to a total dose of 40.0 Gy, [26]. The dose prescription and normal tissue constraints were therefore adopted from the PACE-B trial. Since no intraprostatic boost is applied in our study, a lower dose to normal tissues is expected compared to the PACE-B trial [26, 34].

Risk body	Normal tissue constraints
rectum	V18.1 Gy < 50%, V 29 Gy < 20%, V 36% < 1cc, V 38.5 Gy < 0.2cc
bubble	V 18.1 Gy < 40%, V 37 Gy < 10 cc, optimum: V 37 Gy < 5 cc
Small intestine	V 18.1 Gy < 5cc, V 30 Gy < 0.01 cc
Urethra (Pars prostatica)	Avoidance of central hotspots, Dmax <37.5 Gy, D50% <36 Gy
PRV Urethra	urethra + 2 mm; D0.1cc < 41 Gy; D0.2cc < 37.5 Gy
Femoral heads	V 14.5 Gy < 5%
Bulbus penis	V 29.5 < 50%

Adapted and modified from [26].

### 6.7.3 Normal tissue constraints for moderately hypofractionated radiotherapy of the prostate:

The irradiation regimen used in this study is based on the CHHiP trial, in which fractionation of 20 x 3.0 Gy up to a total dose of 60.0 Gy was performed [27]. The dose prescription and normal tissue constraints were therefore taken from the constraints of the CHHiP trial [35, 36].

Risk body	Normal tissue constraints V60
rectum	Gy $\bar{y}$ 0.01%, V57 Gy $\bar{y}$ 15%, V40 $\bar{y}$ 60%; Circumference Dmax <30 Gy
bubble	V60 $\bar{y}$ 5%, V48 $\bar{y}$ 25%, V40 $\bar{y}$ 50%
Small intestine	V0.01 cm  < 52.7 Gy
Urethra (Pars prostatica)	V40 $\bar{y}$ 50%, Dmax 61 Gy
Femoral heads	V40 $\bar{y}$ 50%
Bulbus penis	V40 $\bar{y}$ 50%

Adapted and modified from [35].

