## 6.2 Guidelines for radiotherapy

The study involves irradiation using two irradiation schemes.  
planned (the applied scheme is recorded in the CRF):

- 1) Radiation therapy of the prostate
  - 5 x 7.25 Gy up to a total dose of 36.25 Gy (MRI-guided on the MR-Linac once daily, 2-3 days per week)
  - If the conditions for ultra-hypofractionated radiation therapy (MR-guided radiation therapy) are not guaranteed at the respective center, radiation therapy can be performed according to the respective departmental standard, e.g. analogous to the STAMPEDE study with e.g. 6 x 6.0 Gy or moderately hypofractionated analogous to the CHHiP protocol with 20 x 3.0 Gy up to a total dose of 60.0 Gy.

- 2) Radiation therapy for bone and lymph node metastases

- Analogous to department-internal standard, e.g. 3 x 9.0-10.0 Gy or 5 x 6.0-7.0 Gy at Lymph nodes (bulks) (once daily, 2-3 days per week)
- Alternatively, in cases of multiple lesions or large central venous extent, fractionation with, for example, [methods] is possible. 5 x 6.0 Gy, dosed to the 80% isodose, is recommended.
- If stereotactic radiotherapy of the metastases is not possible due to anatomical proximity to OARs, metastasis size, or proximity to any previous irradiations, moderately hypofractionated radiotherapy of the metastases can be performed according to an established standard of the respective center.

The decision regarding the fractionation scheme rests with the treating center and its established standard. SBRT (e.g., 3 x 9.0–10.0 Gy) should be preferred over moderate hypofractionation. Whether this is feasible is determined based on the anatomical location, the size of the metastases, any potential risk to the patient's status, and the expected normal tissue exposure. Stereotactic radiotherapy is only possible if the limits for organs at risk are not exceeded (see Section 6.3 Treatment Planning).

The radiation therapy should be administered as IMRT with daily IGRT.

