#### 6.4.1 Pelvic organs at risk during prostate irradiation

The following OARs should be contoured for planning prostate radiation therapy:

OAR	CT/MRI	definition
bubble	CT/MRI	Bladder in CT scan (including outer wall)
rectum	CT/MRI	Analog RTOG (starting from the lowest level of the ischial tuberosity, cranial end in the region of the rectosigmoid junction, penile bulb (part of the
Bulbus	CT/MRI (T2w)	spongiosum bulb) under the urogenital diaphragm [29] best visualized in mpMRI (T2w)
right femoral head	CT	Right femoral head
left femoral head	CT	Left femoral head
pubis	CT	symphysis and pubic bone
Colon	CT	Contour the colon, provided the colon is 2cm above the The highest axial PTV layer is included
Small intestine	CT scan, possibly with MRI	Contour the small intestine if the small intestine is contained 2 cm above the highest axial PTV layer.
urethra	MRI (T2w)	Prostatic urethra from the upper surface of the urethra bulb to the junction with the prostate gland and its opening into the bladder (in mpMRI)

\* in anatomical positional relationships

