### 6.6.2 Target volume definition for moderately hypofractionated radiotherapy of the prostate:

The target volume definition for moderately hypofractionated radiotherapy of the prostate is analogous to the CHHiP trial, taking into account the current ESTRO-ACROP recommendation [27, 30]. If radiotherapy is chosen according to the respective departmental standard (e.g., analogous to the STAMPEDE study), the prescriptions and dose constraints of the respective department apply.

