#### *Clinical target volume (CTV)*

CTV_6000	Prostate + any extracapsular tumor
CTV_5700+SB*	CTV_6000 + SB

\* if T3b or T4 stage with seminal vesicle involvement

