#### *Planning target volume (PTV)*

PTV_6000	CTV_6000 + 6 mm/5 mm dorsal (rectum)
PTV_5700+SB*	(CTV_6000 + SB) + 6mm/5 mm dorsally (rectum)

In the RIALTO study – unlike the CHHiP trial, which used 3D conformal radiation therapy with three weekly position checks based on the bony structures of the pelvis – IGRT with daily verification (CBCT with prostate position check) and the prescription of normal tissue constraints as part of IMRT. Therefore, bowel distension staging analogous to CHHiP is not required for radiation therapy in the present study, as the settings are verified daily and adjusted based on IGRT position.

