## 6.7 Dosage prescription and dose limits

### 6.7.1 Dosage Prescription

Target volume	Dose prescription
Prostate UHF	PTV_3625: 36.25 Gy in 7 Gy per fraction; D98% (PTV_3625) $\ddot{y}$ 33.25 Gy, D99% (CTV_3625) $\ddot{y}$ 34.5 Gy; D50% $\ddot{y}$ 35 Gy PTV_3000: 30 Gy in 6 Gy per fraction; D98% (PTV_3000) $\ddot{y}$ 28.5 Gy; D99% (CTV_3000) $\ddot{y}$ 28.5 Gy; D50% $\ddot{y}$ 30 Gy
Prostate MHF	PTV_6000: 60 Gy in 3 Gy per fraction; D99% (PTV_6000) $\ddot{y}$ 5 Gy, D98% (CTV_6000) $\ddot{y}$ 57 Gy; D1% $\ddot{y}$ 63 Gy; D50 = 60 Gy + 1% PTV_5700: 57 Gy in 2.85 Gy per fraction; D98% (PTV_5700) $\ddot{y}$ 51.3 Gy, D98% (CTV_5700) $\ddot{y}$ 54.15 Gy
Metastases SBRT	PTV min. 80% of the prescribed dose. GTV recorded at min. 95% of the prescribed dose; the maximum should be 120%. The prescribed dose should not be exceeded.
Metastases NF or MHF PTV D98%	90% of the prescribed dose, D2% <107%, CTV D98% - 95% of the prescribed dose, D2% < 110%. Global maximum <115%.

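### Section 6.7.3 limits the prostatic urethra to V40 50% for 20 x 3.0 Gy, a limit that plans meeting the whole-prostate 60 Gy prescription could not generally satisfy

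*Protocol*

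**What the plan says.** Section 6.2 allows, where MR-guided ultrahypofractionation is not available, prostate treatment "moderately hypofractionated analogous to the CHHiP protocol with 20 x 3.0 Gy up to a total dose of 60.0 Gy". Its target, prescription and organ limits are set out in three places:

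- **Target (6.6.2).** CTV_6000 is "Prostate + any extracapsular tumor". PTV_6000 adds 6 mm, or 5 mm towards the rectum. The urethra is not subtracted, and no planning-risk volume or reduced-dose sub-volume is given for it.
- **Prescription (6.7.1).** "PTV_6000: 60 Gy in 3 Gy per fraction", with CTV D98% at 57 Gy and D50 at 60 Gy with a 1% tolerance.
- **Organ limit (6.7.3).** Prostatic urethra: "V40 $\bar{y}$ 50%, Dmax 61 Gy". The sign after V40 is damaged in extraction.

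Section 6.4.1 defines the contour to which the limit applies: "Prostatic urethra from the upper surface of the urethra bulb to the junction with the prostate gland", continuing to its opening into the bladder.

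For comparison, the urethra limit for 5 x 7.25 Gy in section 6.7.2 is "Avoidance of central hotspots, Dmax <37.5 Gy, D50% <36 Gy". That table also gives a urethral planning-risk volume.

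**The concern.** The prostatic urethra runs through the target. A V40 limit of 50% asks for half of it to receive no more than two thirds of the dose prescribed to the gland around it. The target definition contains nothing that would let a planner deliver this.

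A centre using 20 x 3.0 Gy would therefore face two instructions that it cannot generally follow together. It could treat the urethra limit as a missed goal, in which case the table does not guide planning. Or it could enforce the limit and carve a cold track through the middle of the prostate, in a trial whose aim is ablation of PSMA-positive disease. The same cell would be read differently at different centres, and section 4.4 targets six of them.

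**Working it through.** **Inputs from the Protocol.** Prescription 60 Gy in 20 fractions; CTV D98% 57 Gy; D50 60 Gy; PTV margin 6 mm (5 mm dorsally) (6.6.2, 6.7.1). Urethra V40 50% and Dmax 61 Gy (6.7.3). Five-fraction prescription 36.25 Gy with urethra D50% <36 Gy and Dmax <37.5 Gy (6.7.2).

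**Step 1: direction of the limit.** The same damaged sign appears in the rectum and bladder rows of 6.7.3, where only an upper limit makes sense. A lower limit on V40 would not protect an organ at risk. The entry is read as V40 ≤ 50%.

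**Step 2: what it means.** V40 ≤ 50% is the same as a median urethral dose of at most 40 Gy.
- 20 x 3.0 Gy: 40/60 = 66.7% of prescription.
- Dmax in the same cell: 61/60 = 101.7%.
- 5 x 7.25 Gy: D50% limit 36/36.25 = 99.3%; Dmax limit 37.5/36.25 = 103.4%.

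The maximum in the same cell and both limits in the five-fraction table fit a urethra treated at about full dose. The V40 entry alone does not.

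**Step 3: can part of the urethra lie outside the target?** Assumptions, not in the Protocol: spherical CTV of 25 to 80 cc crossed by the urethra along its diameter (3.6 to 5.3 cm), with 0 to 1.5 cm of contoured urethra beyond the gland. The first 0.6 cm beyond the CTV is still PTV, so the share outside the PTV is (e − 0.6)/(L + e).
- e = 0: 0%.
- e = 1.0 to 1.5 cm: about 6% to 18%.

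The share needed is 50%. A plan meeting the prescription would have a urethral V40 of roughly 80% to 100%.

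**Step 4: can the 2% allowance absorb the rest?** CTV D98% at 57 Gy lets 2% of the CTV be colder. By bare volume, half of a thin urethra can fit: for 40 cc and a 5 mm urethra lying wholly in the gland, half the length is 2.12 cm, giving π × 0.25² × 2.12 = 0.42 cc, or 1.0%. But dose cannot step from 40 to 57 Gy at the urethral wall. With a fall-off of g% of 60 Gy per mm, the shell between the two is (17/60 × 100)/g mm: 2.8 mm at 10%/mm, 5.7 mm at 5%/mm, 9.4 mm at 3%/mm. The CTV volume below 57 Gy is then

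π × (d/2 + shell)² × (0.5 × (L + e) − e),

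where d is the urethral diameter and all of e is credited as already spared.

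| CTV | d | e | Fall-off | CTV below 57 Gy |
|---|---|---|---|---|
| 80 cc | 5 mm | 1.5 cm | 10%/mm | 1.72 cc = 2.1% |
| 40 cc | 5 mm | 1.5 cm | 10%/mm | 1.23 cc = 3.1% |
| 40 cc | 7 mm | 1.0 cm | 5%/mm | 4.28 cc = 10.7% |
| 40 cc | 10 mm | 0 | 3%/mm | 13.91 cc = 34.8% |
| 25 cc | 10 mm | 0 | 3%/mm | 11.89 cc = 47.6% |

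Over the whole grid (25 to 80 cc, 5 to 10 mm, 0 to 1.5 cm, 3% to 10% per mm) the result runs from 2.1% to 48%, above 2% throughout.

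**The case against.** **A strict contradiction.** A reader might infer that the 40 Gy limit directly contradicts 57 Gy at D98% and 60 Gy at D50. It does not. Those figures describe the target and the limit describes a thin structure within it, so gaps of 17 and 20 Gy compare different things. The 2% allowance exists, and infeasibility needs geometry that the Protocol does not give. The result also depends on the bounds: at 100 cc, with the other inputs of the most favourable case, the figure is 1.9%, inside the allowance. That case credits the full 1.5 cm beyond the gland as spared. Crediting only the 0.9 cm outside the PTV gives a length of 2.73 cm, 2.44 cc and 2.4%; on that footing the goals become compatible only at about 135 to 140 cc. What stands is that the limit is generally unattainable, not that it is impossible.

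**Damaged table.** Signs are lost, and one rectum entry has slipped into the column header. The fault could lie in the reading of the table. But the urethra cell is legible apart from its sign and also holds a plausible urethral maximum. This justifies a check against the original first.

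**A copied cell.** Femoral heads and penile bulb carry the same V40 50%, which might suggest copying. The bladder row ends with it too, and a repeated figure fits deliberate use equally well. The Protocol does not show how the entry arose.

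**Departmental standard.** Section 6.6.2 says that for departmental schedules "the prescriptions and dose constraints of the respective department apply", and the synopsis describes the alternative, including 20 x 3.0 Gy, as following departmental standard. The wording is mixed. But 20 x 3.0 Gy has its own targets, prescription and constraint table, so the clause does not clearly exempt it.

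**Harm to patients.** A reader might infer that central underdosage will follow. Nothing ranks this limit above coverage, so a missed planning goal is the likelier outcome, and the 61 Gy maximum still caps the urethra.

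**Conclusion.** Wrong as written, and minor. The V40 50% entry sets the median urethral dose at 66.7% of prescription inside a target that is to receive 60 Gy throughout, with no volume defined for sparing. The companion limits point to near-full urethral dose as the intention. That both goals cannot generally be met rests on the assumed gland size, urethral width, extraprostatic length and dose fall-off above, and on the cell being printed as extracted with an upper-limit sign.

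The reach is the 20 x 3.0 Gy fallback only. The Protocol does not say how many patients will receive it, so the range is 0 to 27. Five-fraction plans, departmental schedules with their own constraints, the sample size and the primary test are unaffected.

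**What to change.** Check the urethra cell of section 6.7.3 against the original table. If it is printed as shown here, delete the V40 50% entry and keep the 61 Gy maximum. The cost is one table cell in a protocol amendment, with no change to visits, sample size or analysis.

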### 6.7.4 Normal tissue constraints for SBRT of metastases

The constraints for stereotactic radiotherapy are based on the guidelines for normal tissue exposure in stereotactic procedures and depend on the dose per fraction. Therefore, radiotherapy within the study is performed according to the standard of the respective site.

### 6.7.5 Normal tissue constraints for normofractionated/moderately hypofractionated radiotherapy of metastases

For moderately hypofractionated and normofractionated radiotherapy, department-specific standards also exist, which are based on volume, location, and possible pre-existing conditions and which must be adhered to when irradiating metastases.

Deviations

should be recorded in the eCRF.

## 7. Clinical examinations (visits)

### 7.1 Overview of the accompanying investigations

The following CRF plan, Fig. 2, provides an overview of the accompanying investigations (study visits, PSA follow-up, QoL questionnaires, toxicity assessment, etc.):

	ADT + ARPI		PSMA-PET/CT	Therapie	Follow-Up												
Studienvisite	0	1		2	3	4	5	6	7	8	9	10	11	12	13	14	15
					1 Mo.	3 Mo.	6 Mo.	9 Mo.	12 Mo.	15 Mo.	18 Mo.	21 Mo.	24 Mo.	27 Mo.	30 Mo.	33 Mo.	36 Mo.
Intervention				SBRT Prostata			SBRT Met.										
Prüfung Ein- und Ausschlusskriterien		x															
Aufklärung und Einverständnis		x															
Registrierung		x															
Patientendatendokumentation		x															
Erhebung PSA-Wert	x	x			x	x	x	x	x	x	x	x	x	x	x	x	x
PSMA-PET/CT		x					x				x						
Dokumentation Lebensqualität		x		x	x	x	x	x	x	x	x	x	x	x	x	x	x
Dokumentation Nebenwirkungen				x	x	x	x	x	x	x	x	x	x	x	x	x	x

**Fig. 2:** Schedule of study-specific examinations. Study visits take place at the beginning of the radiation therapy, during the radiation therapy itself, and at the end of the radiation therapy.

## 7.2 Study visits conducted

Specifically, the following parameters will be collected:

- 1) Examination at study enrollment: PSA level (current and trend), biopsies, staging examinations performed, and previously initiated systemic therapy. Assessment of baseline symptoms according to CTCAE v.5, EPIC, IPSS, and IIEF-5, as well as completion of the quality-of-life questionnaires (EORTC QLQ-C30, QLQ-PR25, and EQ-D5). Performance of a PSMA-PET/CT scan.
- 2) Weekly regular doctor consultations will be conducted concurrently with radiation therapy. At the start and end of radiation therapy, side effects will be assessed according to CTCAE v.5, EPIC-26, IPSS and IIEF-5, as well as quality of life (patient-reported: EORTC QLQ-C30 Prostate, QLQ-PR25, EQ-D5).
- 3) PSA levels should be monitored every 3 months via blood test until 30 months after completion of the last radiotherapy for metastases. This can be done at the center or in an outpatient setting, but due to potentially different underlying testing methods, it should preferably always be performed by the same provider, i.e., either at the center during the study visit or by the treating urologist/general practitioner.

In addition, quality of life (patient-reported: EORTC QLQ-C30 prostate, QLQ-PR25, EQ-D5) and possible side effects according to CTCAE v.5, EPIC-26, IPSS and IIEF-5 are recorded quarterly.

## 7.3. PSMA-PET/CT

At study enrollment, a PSMA-PET/CT scan is performed to identify metabolically active lesions and for radiotherapy planning. The PSMA-PET/CT scan is evaluated using standardized criteria based on RECIP [21] or PROMISE V2 [22]. Six months after prostate irradiation, metabolically active lesions are again identified using PSMA-PET/CT. The imaging response after prostate irradiation and of metabolically active metastases is monitored with a repeat PSMA-PET/CT scan 18 months after completion of prostate irradiation. If the PSA levels rise above 2 ng/ml or the PSA doubling time is less than 6 months, this PSMA-PET/CT scan is performed earlier. If individual metastases suitable for radiotherapy are identified, they are treated according to the study protocol.

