## 4.2 Overview of the study interventions

A graphical overview of the planned study interventions and the study procedure is shown in Figure 1. In summary, the prostate will be irradiated using MRI-guided, ultra-hypofractionated radiotherapy analogous to the PACE-B trial with 5 x 7.25 Gy on alternating days (or moderately hypofractionated with 20 x 3.0 Gy on five days/week or analogous to the department's internal standard, e.g., 6 x 6.0 Gy analogous to the STAMPEDE trial), followed six months later by ablative radiotherapy of all remaining metabolically active lymph node and bone metastases. In addition, a total of three PSMA-PET/CT scans are planned for radiotherapy planning and for assessing the radiological response according to RECIP (primary endpoint). Should a PSA increase occur during follow-up according to Phoenix criteria, the planned PSMA-PET scan will be performed earlier. In the case of isolated findings, repeat stereotactic radiotherapy will be considered. In the event of systemic progression and/or the occurrence of visceral metastases, the patient will be presented to the tumor board and the systemic therapy will be changed according to the recommendation made.

A risk-benefit assessment of the planned investigations and interventions is detailed below.

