## 4.3 Risk-benefit assessment of the implemented measures

### 4.3.1 PSMA-PET/CT:

**Planned Examination:** A total of three PSMA-PET/CT scans are planned. For the respective radiation treatment planning (radiation of the prostate and metabolically active metastases), a PSMA-PET/CT scan will be performed at t1 and t2, 6 months apart. In addition to providing the PET data for radiation treatment planning, these PSMA-PET/CT scans will also be evaluated according to RECIP. To assess the primary endpoint – imaging response as seen in the PSMA-PET/CT scan – another PSMA-PET/CT scan will be performed 18 months after prostate radiation treatment.

**Rationale:** According to the S3 guideline, performing a PSMA-PET/CT scan is indicated for radiation therapy planning and for monitoring the treatment response during ongoing systemic therapy in metastatic disease.

Situation [3]. The results of several studies support the use of PSMA-PET/CT for radiotherapy planning, as it achieves higher specificity and sensitivity than the combination of CT and whole-body bone scintigraphy [19, 21, 28]. PSMA-PET/CT is also approved for assessing treatment response to systemic therapy, as is the case in the patient cohort studied here. The RECIP criteria have been validated as a standardized evaluation method for assessing response to radioligand therapy in the polymetastatic setting.

**Procedure and specific risks:** During a PET/CT scan, a radioactive tracer that selectively binds to PSMA and can therefore identify prostate cancer cell metastases with high specificity is injected. The scan lasts a maximum of two to three hours, during which the patient should lie still in the scanner. Specific risks for the patient, which occur rarely to very rarely, include local vein injury with hematoma formation due to phlebotomy when establishing venous access, infections at the injection site, allergic reaction to the tracer and/or contrast agent, general skin, tissue, or nerve damage due to positioning and immobilization, extravasation of the tracer with local tissue reaction, panic attack in patients with claustrophobia, and deterioration of kidney function and triggering of hyperthyroidism due to CT contrast agents. During a PET/MRI scan, exposure to the magnetic field can, in rare cases, cause overheating, headaches,

ringing in the ears or tinnitus may occur. MRI scans should not be performed on patients with a pacemaker or other contraindications to an MRI examination.

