## 5.5 Patient discharge

Patients included in the study can withdraw from the study at any time at their own request and without giving reasons, and without affecting any future treatment or regular follow-up care after radiation therapy.

Exclusion from the study may occur at the discretion of the study physician for reasons of health risk (for example, if a serious comorbidity is present or if the planned radiation therapy is not possible due to prior radiation treatment). In the event of withdrawal from the study, the reason will be documented in the respective patient file and in the eCRF (CRF Drop-Out).

All patients who prematurely withdraw from the study after having already undergone a study intervention should receive a final examination immediately upon withdrawal, which should be documented in the eCRF (CRF Follow-Up). Furthermore, they should be offered a connection to the center as part of their regular radiotherapy follow-up care.

If consent to participate in the study is withdrawn, no further clinical data will be collected and no further study visits will be conducted. If a study intervention has already taken place, continued contact with the center for routine follow-up care after radiotherapy will be offered; no study data will be collected during this follow-up, only routine radiotherapy follow-up care will be provided. All data collected up to this point will be anonymized immediately, unless a request for complete data deletion is received. Treatment plans for treatments already administered within the study must be retained for 30 years in accordance with radiation protection regulations.

A cancellation of the planned study measures may become necessary for the following reasons:

- Disease progression necessitating the initiation of chemotherapy (e.g. Occurrence of visceral metastasis).
- Deterioration of general health, which precludes the continuation of the planned Measures prevented.
- An increase or doubling of the PSA level compared to baseline that is not attributable to a lesion requiring local therapy and necessitates a change in systemic therapy. If PSA progression according to Phoenix criteria is present, the next scheduled PSMA-PET scan is prioritized, and if isolated metastases are found, stereotactic radiotherapy is performed again. In cases of diffuse progression or the presence of visceral metastases, the therapy is adjusted according to the tumor board of the respective center.

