- An increase in metabolically active lesions on PSMA imaging to a degree that prevents the implementation of local therapeutic measures.
- Acute toxicity CTCAE grade 4, showing no improvement.
- PSA doubling time < 6 months without imaging correlation.

If PSA levels rise during follow-up visits, the planned PSMA-PET/CT imaging for diagnostic purposes should be brought forward, and the study outpatient clinic should be consulted to determine whether newly occurring lesions should be treated with further local therapy.

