# 6. Guidelines for radiotherapy

## 6.1 Specifications for systemic therapy (antihormonal therapy according to guidelines)

In accordance with the S3 guideline, the initiation of systemic antihormonal therapy is started six months prior to study screening by the treating urologists (either at a center or in private practice). This involves complete androgen blockade through a combination of ADT and NHT (e.g., apalutamide, enzalutamide, or others, as determined by the primary treating urologist). The choice of drug and NHT is determined by the tumor board or the primary treating urologist, in accordance with the S3 guideline. This is the standard therapy and not part of the study protocol presented here. When initiating long-term hormone therapy, each patient is offered radiation gynecomastia prophylaxis according to departmental standards. Systemic therapy should be initiated at least six months prior to study enrollment and the PSMA-PET/CT scan.

If the PSA level does not fall completely to  $<0.2$  ng/ml and thus the study inclusion criteria are met, systemic therapy will be continued until a significant PSA increase occurs (doubling of the baseline value or PSA doubling time of  $< 6$  months).

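### A PSA rise brings forward the month-18 PSMA-PET that carries the primary endpoint, with no later scan planned, and the trigger differs between sections 4.2, 5.5 and 7.3

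*Protocol*

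**What the plan says.** **The scan.** Protocol section 4.3.1 plans three PSMA-PET/CT scans. For the primary endpoint, "another PSMA-PET/CT scan will be performed 18 months after prostate radiation treatment". Fig. 2 in section 7.1 shows PET at enrolment, month 6 and month 18 only. Section 4.4 reads RECIP response 12 months after metastasis-directed therapy.

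**Bringing it forward.** Four sentences do this:
- Section 4.2: "Should a PSA increase occur during follow-up according to Phoenix criteria, the planned PSMA-PET scan will be performed earlier".
- Section 5.5, in the list of reasons for cancelling study measures: "If PSA progression according to Phoenix criteria is present, the next scheduled PSMA-PET scan is prioritized".
- Section 5.5, closing paragraph: "If PSA levels rise during follow-up visits, the planned PSMA-PET/CT imaging for diagnostic purposes should be brought forward".
- Section 7.3, directly after describing the month-18 scan: "If the PSA levels rise above 2 ng/ml or the PSA doubling time is less than 6 months, this PSMA-PET/CT scan is performed earlier".

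**What may follow an early scan.** Section 7.3 continues: "If individual metastases suitable for radiotherapy are identified, they are treated according to the study protocol". Under section 6.1, "systemic therapy will be continued until a significant PSA increase occurs", which that section defines as a doubling of the baseline value or a doubling time under 6 months. Section 5.5 also lists "PSA doubling time < 6 months without imaging correlation" as a reason to cancel study measures.

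**The concern.** A diagnostic scan prompted by rising PSA uses up the scan that decides the trial. Patients doing badly by PSA are read early and the others at month 18, so the time of reading is tied to outcome. The protocol does not say whether the early reading replaces the month-18 reading.

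The bias has no fixed direction. An early scan may come before regrowth that month 18 would have shown, or may be too early for a patient who would have responded by then. The endpoint in 3.1 is a PSMA volume reduction of at least 30% in the initially PSMA-expressing lesions. A patient whose PSA rises because of a new lesion elsewhere could therefore still be read as a responder.

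A separate problem is that the rule for moving the scan is not the same in each section. Centers could scan the same PSA course at different times. Section 10.2 refers ambiguities to the study center, but the text gives the center no single rule to apply. In a single arm of 27 patients, one or two readings can change the result.

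**Working it through.** **1. Which scan moves.** Metastasis radiotherapy is at month 6 after prostate radiotherapy (4.2, Fig. 2). Month 6 + 12 months (4.4) = month 18, the scan in 4.3.1. After metastasis radiotherapy this is the only planned PET left, so it is the one that a trigger moves.

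**2. When a triggered patient is read.** Fig. 2 takes PSA at months 9, 12 and 15 between the second and third PET:
- 9 − 6 = 3 months
- 12 − 6 = 6 months
- 15 − 6 = 9 months

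Section 4.4 requires 12. No later PET appears in Fig. 2.

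**3. The triggers side by side.**

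| Section | Trigger |
|---|---|
| 4.2 | Phoenix criteria (not defined in the protocol) |
| 5.5, list | Phoenix criteria (not defined) |
| 5.5, close | PSA rise, no threshold |
| 7.3 | PSA above 2 ng/ml, or doubling time under 6 months |

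An example with assumed values needs no Phoenix definition. PSA goes from 0.8 to 1.0 ng/ml in 3 months, a doubling time of 3 × ln 2 / ln(1.0/0.8) = 9.3 months. Read literally, the close of 5.5 moves the scan and 7.3 does not. Entry PSA has a lower limit of 0.2 ng/ml (5.2) and no upper limit, so a patient may enter already above 2 ng/ml.

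**4. The plan's own sample size.** Inputs from 4.4: null rate 0.15, target rate 0.40, one-sided alpha 0.05, power 90%, n = 27. Exact binomial:
- P(X ≥ 7 | 27, 0.15) = 0.0986, too large.
- P(X ≥ 8 | 27, 0.15) = 0.0398.
- P(X ≥ 8 | 27, 0.40) = 0.9047.

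Success at 8 or more of 27 reproduces the stated alpha and power. With n = 26 and the same cut-off, power is 0.878, so 27 reproduces as well. The figures below use this inferred cut-off, not the 5/27 wording printed in 4.4.

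**5. Early readings that make non-responders look like responders.** Suppose k patients are certain non-responders read early as responders, and the rest respond at 0.15. Type I error = P(Bin(27 − k, 0.15) ≥ 8 − k):
- k = 1: 0.083
- k = 2: 0.162

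**6. Triggered patients counted as non-responders.** Take k = 5 (assumed), with the cut-off still 8 of 27.
- If they would have responded at 0.40 like everyone else: P(Bin(22, 0.40) ≥ 8) = 0.710.
- If they would not have responded anyway and the overall rate stays 0.40, the other 22 respond at 27 × 0.40 / 22 = 10.8/22 = 0.491: P(Bin(22, 0.491) ≥ 8) = 0.921.

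On the second assumption power is 0.907 for k = 1 and 0.949 for k = 10, so none is lost.

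**The case against.** The best defence is that 7.3 has a plain meaning: the response scan itself moves, so the early scan is the reading. Scanning when PSA rises, so that treatment can follow, is deliberate and fits a three-scan plan reported to the radiation protection authority (synopsis, 9.3). How a moved scan is classified could be left to a SAP, which is not at hand. Part of this stands. PSA-triggered imaging is reasonable care, and the early scan may well be the intended reading. But section 4.4 still fixes the decision at 12 months after metastasis-directed therapy, and a SAP cannot reconcile clinical triggers that differ within the protocol.

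A reader might infer more than the documents support:
- *The differing triggers cause the missing scan.* They do not. Moving the scan causes it, and 4.2, 5.5 and 7.3 all do that. The wording only affects which patients are moved.
- *The 2 ng/ml limit contradicts Phoenix.* The protocol does not define Phoenix, so this cannot be settled from it. What can be shown is that 7.3 adds a doubling-time limb absent from the Phoenix sentences, and that the close of 5.5 has no threshold. That close could be read as a loose summary of the criteria before it, which would weaken the 0.8 to 1.0 example.
- *A fourth PET is required.* It would give a fixed reading time, but it is an extra procedure and a design preference.
- *Re-irradiation of new lesions or a change of systemic therapy must count as failure.* Section 3.1 is limited to the initially PSMA-expressing lesions, so this would widen the endpoint.
- *Power falls to 0.71.* That is one end of a range. Patients with rising PSA may well be non-responders anyway, and then no power is lost.

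**Conclusion.** The point holds as two linked but separate defects. First, followed as written, the protocol reads the primary endpoint at about 3, 6 or 9 months after metastasis-directed therapy in triggered patients and at 12 months in the rest. This conflicts with 4.4, and no later scan is planned. Second, the sections do not give one PSA rule for moving the scan.

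The size is illustrative. It rests on the inferred cut-off of 8 in 27 and on assumed numbers of affected patients. Within those assumptions, one or two misread patients double or quadruple the type I error of 0.040 (to 0.083 or 0.162). Counting five triggered patients as non-responders gives power anywhere from 0.710 to 0.921. The net direction cannot be derived from the documents. This should be corrected before month-18 readings begin, so that the choice of reading is not made with results in view.

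**What to change.** 1. Use one PSA trigger for the early PET in 4.2, in both places in 5.5, and in 7.3. Define it relative to nadir or baseline, because entry PSA has no upper limit.
2. State in 3.1 and 4.4 that the primary reading is the month-18 PET, and that RECIP progression on a triggered PET before then counts as non-response.
3. For a triggered patient without progression, make the early PET the primary reading, and report non-response imputation for these patients as a sensitivity analysis.
4. Leave to the sponsor whether re-irradiation of new lesions or a change of systemic therapy also counts as non-response. If so, say in 3.1 that the endpoint is widened.

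The cost is an amendment of 3.1, 4.2, 4.4, 5.5 and 7.3, with no extra scan. The observed response rate may fall slightly, and an outcome-dependent reading time remains for triggered patients without progression. The sponsor should estimate how many patients are likely to be triggered before adopting the rule.
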